PROTOCOLE INTRA OBS PROT ID: 2009/OBS-01 NCT: NCT04414202 Date: 15 Dec 2019

Date	: 15 Dec 2019	
₩	TITLE	INTRA-OBS: Observational study of intra-operative partial irradiation of invasive ductal breast carcinomas with a good prognosis Protocol ID: 2009/OBS-01 N° NCT: NCT04414202
₩	SPONSOR	CRLC [Regional Anti-Cancer Center] Val d'Aurelle [name]
♦	COORDINATOR	Dr [name] CRLC [Regional Anti-Cancer Center] Val d'Aurelle [name] [contact]
♠	INDICATION	Invasive breast cancer with a good prognosis that is accessible to breast-conserving surgery.
₩	METHODOLOGY	Monocentric observational study
 	RATIONALE	Due to screening, T1N0 early-stage breast cancer now accounts for more than 50% of the tumors diagnosed in France. The prognosis of these tumors is good, even excellent in women ≥ 65 years of age, with specific survival of 98% at 5 years. The treatment of these tumors most often combines breast-conserving surgery and external whole breast irradiation for 6.5 weeks. A true de-escalation of treatment is taking place with these tumors, both surgically and medically. Surgery therefore now prefers breast-conserving methods in combination with exeresis of the sentinel lymph node only. In the same way, in many international studies, radiotherapy has been evaluating the possibility of reducing both: - the irradiation volume at the excision site (partial irradiation) - the duration of this irradiation (accelerated radiotherapy) Between 2004 and 2007, the CRLC [Regional Anti-Cancer Center] thus evaluated the feasibility and the oncological results of intra-operative partial irradiation via a phase II study in women 65 years of age and older with T1N0M0 hormonesensitive tumors with a good prognosis. From 2010 to 2013, the ICM carried out an observational study of these tumors with an excellent prognosis. In July 2009, the American Society for Radiation Oncology (ASTRO) published a consensus statement with specific recommendations and indications for accelerated partial breast irradiation (APBI). This APBI technique has been developing in France over the past 5 years within the framework of clinical studies and in compliance with the 2012 recommendations of the French National Cancer Institute. This APBI can be given by 3D external radiotherapy or, as in this study, by intra-operative radiotherapy (IORT) in order to obtain optimal precision and spare as much of the surrounding healthy tissue as possible.

PROTOCOLE INTRA OBS PROT ID: 2009/OBS-01 NCT: NCT04414202 Date: 15 Dec 2019

Date : 10 Dec 2019		
	We therefore propose a cohort study to prospectively analyze the results of this technique applied to the indications strictly defined by the ASTRO.	
	Primary: Local intra-mammary relapse rate	
♦ OBJECTIVES	Secondary: - Cosmetic results - Survival without metastatic relapse - Satisfaction of the patient with regard to her treatment - Impact of the accelerated treatment on the maintenance of autonomy in elderly patients	
♥ PATIENT SELECTION	INCLUSION CRITERIA: Women 60 years of age or older, - Histologically proven invasive ductal breast cancer or of a histologically favorable sub-type (mucinous, tubular or colloid), Unifocal tumor, - T1 (diameter ≤ 20 mm), - N0 (pN0 or pNi+), - M0, - Gland exeresis margins ≥ 2 mm, - Estrogen receptor positive, - Information and non-opposition of the patient. EXCLUSION CRITERIA: Inflammatory breast cancer, - Associated peri-tumoral lymphatic - Associated extensive intra-ductal component - Invasive lobular carcinoma - Pure ductal carcinoma in situ, - Sarcoma or lymphoma-type non-epithelial tumor - Synchronous bilateral breast cancer, - Any prior neo-adjuvant treatment: radiotherapy, chemotherapy, hormone therapy	
♥ TREATMENT	The treatment combines extended tumorectomy with axillary dissection (sentinel lymph node) in addition to 20 Gy of peroperative partial irradiation at the tumor site.	
♥ NUMBER OF PATIENTS	The number of patients is based on a recruitment potential of 50 patients per year for 3 years, i.e. 150 patients.	
STATISTICAL ANALYSIS	We seek to demonstrate that the intra-mammary relapse rate is not increased, i.e. a local relapse rate for patients over 60 years of age of between 4 and 7.3% at 10 years.	
♥ STUDY PERIOD	3 years of inclusion. 10 years of follow-up.	

PROT ID: 2009/OBS-01

NCT : NCT04414202 Date : 15 Dec 2019

2- STUDY RATIONALE

Breast carcinoma remains the most common cancer in women in France, where it is currently a major

public health issue, accounting for 37% of new cases of cancer (1).

Its incidence increases considerably and regularly between 30 and 60 years of age, reaching a

maximum plateau (at 320 cases in 100 000) in women 60 to 80 years of age (2).

At the same time, breast cancer mortality has been decreasing since 1980 thanks to the improvement

in treatments along with earlier diagnosis (1).

Therefore, the early pT1N0 stages (diameter ≤ 2 cm without lymph node involvement), which currently

account for 50 to 60% of diagnosed tumors (1), have a specific survival of 88% at 5 years. This

percentage rises to 96% in patients 65 years of age and older (4).

From a therapeutic standpoint, over the past 30 years, many international studies (5-7) have

demonstrated that the combination of breast-conserving surgery and external radiotherapy administered

over the entire breast was equivalent to mastectomy in terms of survival. It has now also been shown

that the addition of this adjuvant radiotherapy to breast-conserving surgery increases overall survival (8-

9). Today, this surgery consists of a tumorectomy and axillary sentinel lymph node dissection.

This radio-surgical combination is therefore the most common strategy.

More recently, studies have shown that the addition of supplementary irradiation at the excision site

further reduced the risk of local relapse (10), bringing it down to 6% with no differentiation based on age

after 10 years of follow-up.

Based on this, considering the most often very localized nature of this relapse, over the past years,

many radiotherapy teams have developed the concept of Partial Breast Irradiation (PBI), proposing a

reduction in irradiation volume (reduction in the irradiated volume of the breast, but also of the adjacent

healthy organs such as the underlying heart and lungs).

This partial irradiation therefore allows for an interesting de-escalation of treatment.

Today, it is therefore being evaluated in many international studies using various irradiation techniques

(interstitial curietherapy, MammoSite, intra-operative irradiation or 3D conformal radiation therapy).

At the Montpellier CRLC [Regional Anti-Cancer Center], which has a great deal of experience in intra-

operative irradiation using electron therapy in breast cancer (11-12), we thus conducted a phase II study

PROT ID: 2009/OBS-01

NCT : NCT04414202 Date : 15 Dec 2019

(13) between 2004 and 2007 evaluating the feasibility and reliability of this technique within the

framework of single-dose intra-operative partial irradiation for tumors with an excellent prognosis

(hormone sensitive T1N0M0 invasive ductal carcinoma in patients 65 years of age and older).

With regard to the primary objective, the dosimetric results proved the reliability and reproducibility of

the technique. With regard to the secondary objectives, the oncological results turned out to be good (2

intra-mammary relapses out of 42 patients and 100% of patients alive and disease-free at 30 months).

The cosmetic results were also considered to be good to excellent in 90% of patients.

The immense clinical advantage of this intra-operative technique over the other partial irradiation

techniques is its accelerated mono-fractionated character.

Radiotherapy is thus administered during surgery and relieves the patient of 6 and a half weeks of

demanding, costly, out-patient radiotherapy that elderly patients often have a hard time accepting.

This APBI technique must however only be used in well-defined indications for tumors with an excellent

prognosis for which the risk of occult microscopic disease in the rest of the non-irradiated breast is the

lowest.

It was with this objective that in July 2009 the American Society for Radiation Oncology (ASTRO)

reviewed all of the 4 randomized studies and the 38 published studies conducted between 1993 and

2008 regarding ABPI. This learned society then published a consensus statement (Smith, etc.) that very

precisely defined the characteristics of a group of patients that could routinely benefit from this partial

irradiation outside of a clinical study context.

These criteria correspond to all the points that we have retained for our phase II study conducted at the

Montpellier CRLC, thus validating the routine practice today of partial irradiation for:

• patients ≥ 60 years of age

without known BRCA1/2 genetic mutation

• with an invasive cancer (exclusion of pure ductal carcinoma in situ) histologically proven by

biopsy

invasive ductal type or histologically favorable type (mucinous, tubular, colloid)

• T1: tumor diameter ≤ 20 mm (radiologically on the pre-operative MRI or ultrasound and

extemporaneous measurement)

Clinical N0 (and extemporaneously)

Of any SBR grade

Without vascular or lymphatic emboli (on the pre-operative biopsy)

• With estrogen receptors (ER+)

Having received no neo-adjuvant treatment

PROT ID: 2009/OBS-01

NCT : NCT04414202

Date: 15 Dec 2019

In conclusion, we are thus proposing a monocentric cohort study (this intra-operative technique is only

used in France in this Center) to prospectively analyze the course of all the patients treated with intra-

operative partial irradiation at the Montpellier CRLC.

3-OBJECTIVES OF THE STUDY

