3.1 Primary objective

To evaluate the local relapse rate after local treatment combining extended tumorectomy with axillary

(sentinel lymph node) dissection and per-operative partial irradiation of the tumor bed.

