7.1 Primary endpoint

The primary endpoint of this study is the local relapse rate, defined as the number of intra-mammary relapses in the treated breast (regardless of the quadrant and including the skin) and homolateral lymph

relapses in the treated breast (regardless of the quadrant and including the skirl) at

node, assessed at 10 years.

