7.2 Secondary endpoints

- Study of survival without metastatic relapse, overall survival and specific survival.

- Evaluation of the cosmetic result (annex 4)

- Assessment of the impact of this accelerated treatment on the maintenance of subject's autonomy

using the geriatric scale (ADL, IADL) (annex 3).

-Satisfaction of the patient (annex 4)

8-STATISTIC ANALYSIS

The number of patients is not limited.

However, based on a potential recruitment of 50 patients per year, this study can be analyzed after a

recruitment period of 3 years, or about 150 patients.

The primary assessment will be the rate of intra-mammary relapse, which should remain the same as

after traditional irradiation of the entire breast. This rate of recurrence is estimated in the age series

reported by EORTC (10) between 4 and 7.3% at 10 years for patients over 60 years of age (2 to 3.7%

at 5 years for exponential distribution , with a unilateral confidence interval of 10%). The finding of a

number of relapses 10 / 150 cases at 5 years - during the intermediate analysis - would lead to

questioning this technique.

9- REGULATORY AND ETHICAL ASPECTS

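### The synopsis sets out to demonstrate that relapse is not increased, but about 150 uncontrolled patients, numbered by recruitment, can generally only estimate the 10-year rate

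*Protocol*

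**What the plan says.** The synopsis, under statistical analysis, states the aim as "We seek to demonstrate that the intra-mammary relapse rate is not increased" and explains this as "a local relapse rate for patients over 60 years of age of between 4 and 7.3% at 10 years".

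Section 3.1 is more modest: "To evaluate the local relapse rate after local treatment combining extended tumorectomy with axillary" dissection and partial irradiation. It names no comparator, limit or hypothesis. The synopsis objectives row also lists only the local intra-mammary relapse rate.

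On size, the synopsis says: "The number of patients is based on a recruitment potential of 50 patients per year for 3 years", giving 150. Section 8 says "The number of patients is not limited" and foresees analysis at about 150. Section 4.1 describes a single-centre observational study, with no concurrent control.

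Section 8 takes the 4 to 7.3% from an external series treated with whole-breast irradiation and expects the rate here to stay the same. It converts the range to 2 to 3.7% "at 5 years for exponential distribution , with a unilateral confidence interval of 10"%. Its one decision rule is an interim alarm: a "number of relapses 10 / 150 cases at 5 years - during the intermediate analysis - would lead to" questioning the technique.

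Section 7.1 defines the primary endpoint as intra-mammary relapse in the treated breast together with relapse in the homolateral lymph "node, assessed at 10 years".

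**The concern.** To demonstrate that a rate is not increased is a confirmatory claim. It needs the data to exclude rates that would count as an increase. The synopsis ties the claim to a range of rates, the number of patients was not chosen to exclude anything, and the body of the protocol sets an estimation aim. A reader of the final report could hold the synopsis wording against an observed 10-year rate of, say, 6% and take the claim as established, although the interval around that rate would extend well above the historical range. At stake is whether the study may conclude that partial irradiation does not raise relapse, or may only report a rate with its uncertainty.

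The event is also unclear. The synopsis sentence moves from intra-mammary to local relapse, section 8 speaks of intra-mammary relapse, and section 7.1 adds homolateral nodal relapse. The text does not fix which of these is to be set beside 4 to 7.3%.

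**Working it through.** **Inputs.** n = 50 × 3 = 150 (synopsis); historical range 4 to 7.3% at 10 years (synopsis, section 8); one-sided 10% level (section 8, there attached to the 5-year range). Assumed: all 150 followed to 10 years, exact binomial limits, the 10% level carried over to 10 years, and 7.3% used as the value to exclude for illustration.

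**1. The protocol's own figures.** Under an exponential model the 5-year rate is 1 − (1 − p)^0.5, where p is the 10-year rate. For 4% this is 1 − √0.96 = 2.02%; for 7.3% it is 1 − √0.927 = 3.72%. Both match section 8. The alarm also reproduces: the exact one-sided 90% lower limit is 3.65% for 9/150 and 4.19% for 10/150, so 10 is the smallest count that excludes 3.7%. P(X ≥ 10 | n = 150, 3.7%) = 0.053. Section 8's arithmetic is sound.

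**2. Counts inside the range at 10 years.** 0.04 × 150 = 6.0 and 0.073 × 150 = 10.95, so 6 to 10 relapses lie inside it.

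**3. Upper limits for those counts.** The exact upper limit for x relapses is the (1 − α) quantile of Beta(x + 1, n − x).

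| Relapses of 150 | Observed | Upper limit, α = 10% | Upper limit, α = 5% |
|---|---|---|---|
| 6 | 4.0% | 6.9% | 7.7% |
| 7 | 4.7% | 7.7% | 8.6% |
| 8 | 5.3% | 8.5% | 9.4% |
| 9 | 6.0% | 9.3% | 10.2% |
| 10 | 6.7% | 10.1% | 11.0% |

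At one-sided 10%, only 6/150 excludes 7.3%. At one-sided 5%, no count in the range does.

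**4. Chance of excluding 7.3%.** At one-sided 10% this needs at most 6 relapses. P(X ≤ 6 | n = 150) is 0.606, 0.373 and 0.198 at true rates of 4%, 5% and 6%. At one-sided 5% it needs at most 5 relapses, with probability 0.442, 0.234 and 0.108.

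**5. Number needed for that purpose.** At one-sided 10%, 80% power to exclude 7.3% first requires about 225 fully followed patients if the true rate is 4%, and about 852 if it is 5.5% (an assumed mid-range value).

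Complete follow-up is the favourable case, and the limits above treat 7.3% as known. Losses to follow-up or uncertainty in the historical figure would weaken the claim further.

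**The case against.** The best defence is that the protocol nowhere says an observed rate inside 4 to 7.3% means success. Section 8 presents the range as the historical rate that this cohort is expected to match, and the synopsis may be compressing that into one line about the underlying rate. A literal success rule would even be odd: 0 to 5 relapses, the best results, would fall outside it, which happens with probability 0.44 at a true rate of 4%. This stands. A reader might infer that the protocol commits itself to calling 10/150 not increased; the text does not go that far. The point-estimate reading is therefore only a condition in the argument. The other reading does not save the verb, though: to demonstrate that the underlying rate is at or below 7.3%, the upper limit must lie below it, and step 4 shows how seldom it would.

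An evaluation objective and an expectation of no increase can coexist, and only one verb in one synopsis line is out of tune. That limits the weight of the point, but the line is where the protocol states its statistical aim.

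A maximum acceptable rate and a confidence level at 10 years could be set in an analysis plan that is not shown. Their absence is therefore not the fault raised here. The wording that claims more than section 3.1 is.

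A reader might also infer that silence of the 5-year alarm would be taken as proof of no increase. The protocol never draws that inference; it uses the rule only to question the technique.

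**Conclusion.** The point holds as one of wording and permitted conclusion. The synopsis claims to demonstrate no increase; section 3.1 evaluates a rate; and an uncontrolled cohort of about 150, numbered by recruitment, does not generally support the stronger claim. Four of the five counts inside the historical range leave rates above 7.3% unexcluded at one-sided 10%, and all five do at one-sided 5%. Even if the true rate lies inside the range, the chance of an upper limit below 7.3% falls from 61% at 4% to 20% at 6%.

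These sizes rest on 150 patients with complete 10-year follow-up, exact binomial limits, a 10% level that the protocol states only for 5 years, and 7.3% as the illustrative limit. Section 8 says the number is not limited, so a larger cohort would do better. The 5-year alarm at 10/150 is a sound signal of harm and needs no change on this account. The data remain usable whichever wording is kept, so this should be fixed but does not undermine the study.

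**What to change.** 1. In the synopsis, and in the matching expectation in section 8, restate the aim as estimating the 10-year relapse rate with its confidence interval, set descriptively beside the historical 4 to 7.3%. This agrees with section 3.1.
2. In the same sentences, name the event that is compared with the historical range: intra-mammary relapse alone, or with homolateral nodal relapse as in section 7.1.
3. Keep no increase as a possible conclusion only if the upper confidence limit lies below a maximum acceptable rate that the sponsor fixes and justifies in advance, together with its confidence level. No value is proposed here.

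The cost is a few sentences; rewording adds no patients or visits. The downside is that the protocol gives up the claim to demonstrate, or makes it conditional. If the sponsor kept it with 7.3% as the bound, about 150 patients would miss it more often than not at a true rate of 5% or 6%. A wider bound is easier to meet but would have to be justified as still meaning no increase.

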3.1 Primary objective

To evaluate the local relapse rate after local treatment combining extended tumorectomy with axillary

(sentinel lymph node) dissection and per-operative partial irradiation of the tumor bed.

3.2 Secondary objectives

To study:

Cosmetic results

- Survival without metastatic relapse

Satisfaction of the patient with regard to her treatment.

- Impact of accelerated treatment on the maintenance of autonomy in elderly patients

4-METHODOLOGY

4.1 Study type

This is a monocentric observational study.

4.2 Patient registration

The patients will be seen before surgery at a pre-operative consultation. Information will be given orally

and in writing (annex 2).

After checking the inclusion and exclusion criteria, eligible patients will be registered.

Registration will be carried out by fax ([name]) at the biostatistics coordination center of

the CRLC Val d'Aurelle during the stay in the surgical unit once the results of the extemporaneous

analysis have been obtained.

4.3 Inclusion evaluation

Patients who are eligible for the study must have an initial evaluation during the 10 weeks prior to

registration.

This evaluation will include:

Physical examination

PROT ID: 2009/OBS-01

NCT : NCT04414202 Date : 15 Dec 2019

- WHO index, weight, height

- Bra size (band and cup size)
- 2D tumor size
- ADL and IADL indexes (annexes 4 and 5) evaluated by the investigator or CRA
- Listing of co-morbidities and concomitant treatments

Para-clinical examinations

- Bilateral mammography
- Bilateral breast ultrasound with 2D measurement of tumor size
- Breast MRI may be recommended, but remains optional
- Chest X-ray
- Liver ultrasound or abdominal CT scan
- Bone scintigraphy
- Photograph of both breasts straight on and the profile of the breast to be treated

4.4 Follow-up evaluation during the study

The follow-up of patients treated in the study is conventional monitoring in compliance with the current recommendations.

It will be based on a physical examination every semester for the first 5 years. This clinical follow-up will then be carried out annually from the 6th to the 10th year.

The para-clinical examinations will be limited to annual mammography and breast ultrasound. Breast MRI remains optional. In case of suspected local relapse (clinical and/or radiological), histological confirmation will be obtained.

The evaluation of autonomy (ADL and IADL) (annex 3) as well as the patient satisfaction index (annex 4) will be evaluated at 3 weeks, 6 months and 12 months of treatment to assess its impact.

4.5 End of study evaluation and long-term follow-up

At the end of the 10 years of observation of the study, in compliance with current recommendations, the patients will have annual clinical and radiological monitoring, as usual.

If the patient withdraws or stops the study, the examination will be carried out at the planned date on the follow-up calendar (except for withdrawal from the study for an exceptional reason with conduct of the end of study examination within the 3 days following the withdrawal).

5-PATIENT SELECTION

5.1 Inclusion criteria

- 1. Women 60 years of age or older,
- 2. Histologically proven invasive ductal breast cancer or of a histologically favorable sub-type (mucinous, tubular or colloid),

PROT ID: 2009/OBS-01

NCT : NCT04414202 Date : 15 Dec 2019

3. Unifocal tumor,

4. T1 (diameter \leq 20 mm), as per the pre-operative MRI and/or ultrasound dimensions and after per-

operative confirmation (extemporaneous examination),

5. N0 (pN0 or pNi+),

6. M0,

7. Gland exeresis margins ≥ 2 mm,

8. Estrogen receptor positive,

9. Information and non-opposition of the patient

5.2 Exclusion criteria

1. Inflammatory breast cancer,

2. Associated peri-tumoral lymphatic

3. Associated extensive intra-ductal component

4. Invasive lobular carcinoma

5. Pure ductal carcinoma in situ.

3. Sarcoma or lymphoma-type non-epithelial tumor

7. Synchronous bilateral breast cancer,

8. Any prior neo-adjuvant treatment: radiotherapy, chemotherapy, hormone therapy

6-TREATMENT ADMINISTERED IN THE STUDY

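### Do the missing BRCA1/2 item and the unfinished exclusion 2 let patients outside the ASTRO indication into the cohort?

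*Protocol*

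**What the plan says.** The protocol describes the eligible population in four places.

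- **Synopsis, Rationale.** The technique is to be analysed prospectively as "applied to the indications strictly defined by the ASTRO".
- **Section 2 (Study rationale).** The ASTRO indication is set out as a list. It includes "without known BRCA1/2 genetic mutation", "Without vascular or lymphatic emboli (on the pre-operative biopsy" and "Clinical N0 (and extemporaneously". The section closes by saying that the study will follow every patient given the technique at the centre.
- **Synopsis (Patient selection) and sections 5.1 and 5.2.** These hold the criteria for registration. Neither version mentions BRCA1/2. Exclusion 2 reads "Associated peri-tumoral lymphatic" in 5.2. The synopsis runs straight into the next criterion: "Associated peri-tumoral lymphatic - Associated extensive intra-ductal component".
- **Section 6.4.** The surgeon offers the technique to patients who satisfy recommended criteria, without naming the list, and then invites the patient to take part.

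Section 4.2 ties entry to the criteria: "After checking the inclusion and exclusion criteria, eligible patients will be registered". Registration takes place during the surgical stay, once the intra-operative pathology result is known.

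**The concern.** A cohort said to represent a *strictly* defined indication should have criteria that reproduce it. On paper these do not. A known BRCA1/2 carrier lies outside the indication in section 2, yet nothing in section 5 bars her registration.

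Exclusion 2 cannot be applied literally, because it has an adjective and no noun. Even if emboli is supplied, the line does not say whether vascular emboli count, or whether the biopsy or the operative specimen decides. Brevity does not obviously explain this. For tumour size, 5.1 item 4 does carry over the method of assessment ("as per the pre-operative MRI and/or ultrasound dimensions"), while for emboli 5.2 does not.

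At stake is who makes up the denominator of the local relapse rate. If the biopsy and operative-specimen readings select different women, two people applying the same protocol could assemble slightly different cohorts, and the result would describe a population somewhat different from the one claimed.

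**Working it through.** No arithmetic applies: the point rests on no rate, margin, error level or sample size. The check compares the texts.

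**Step 1: section 2 list against the registration criteria.** Section 2 has ten items.

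- Seven have a counterpart: age, invasive disease (pure in situ carcinoma excluded), ductal or favourable histology, T1, N0, oestrogen receptor positivity and no neo-adjuvant treatment.
- One, any SBR grade, needs no criterion.
- One, emboli, survives only as the unfinished exclusion 2.
- One, known BRCA1/2 mutation, is absent.

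The total is 7 + 1 + 1 + 1 = 10. N0 is worded differently in the two places, but this is not a contradiction. Section 2 describes clinical staging with an intra-operative check, and 5.1 names the pathological categories accepted.

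**Step 2: is the break in exclusion 2 a text-extraction fault?** Probably not. It falls at the same word in a synopsis table and in a numbered list, and the next criterion follows intact both times. A word lost in drafting or translation is likelier, though the PDF itself was not seen.

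**Step 3: can the missing word be recovered?** Section 2 has one item on lymphatic invasion, and it concerns emboli. That is an inference, but the document offers no competing noun. Whether vascular emboli are covered cannot be recovered this way, because exclusion 2 says only lymphatic.

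**Step 4: which specimen?** Section 2 names the pre-operative biopsy. Under 4.2 the criteria are checked before registration, and registration follows the intra-operative result. The biopsy is known by then. Full analysis of the operative specimen (6.3) may come later, and the irradiation is given during the same operation. The biopsy is therefore the natural reading. It is not the only possible one, since 5.1 also uses pathological nodal categories.

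**Step 5: how would a known carrier reach registration?** Under 6.4 the offer of treatment comes first and the invitation second. In the synopsis, recommendations for this technique are those of ASTRO and the French National Cancer Institute, and the protocol never describes its own section 5 as recommended. On that reading the section 2 list operates before registration and removes known carriers. Only if 6.4 is taken to mean section 5 does the path stay open, and that is the weaker reading.

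**Step 6: does any stated figure move?** Section 8 describes the reference relapse rate of 4 to 7.3% at 10 years only by age (over 60), not by BRCA1/2 status or emboli. The warning figure of 10 relapses in 150 cases at 5 years is a count in the registered cohort. Neither is derived from the two items in question.

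**The case for a change.** The strongest case for a change is that eligibility belongs in the protocol and cannot be left to a later analysis plan, and that an exclusion without a noun cannot be applied or audited as written. Section 5 is not simply a short form of section 2. It adds unifocality, a 2 mm margin, extensive intra-ductal component and synchronous bilateral disease, so the missing items look like oversights. Section 6.4 names no list and is not the registration check of 4.2, so it narrows the gap without closing it. Rewording would be cheap and would need no new test or visit.

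Much of this stands as description: the BRCA1/2 item is missing, exclusion 2 is incomplete, the vascular question is open, and 6.4 should ideally say which list it means. What does not stand is the step to a consequence. The additions in section 5 also show that section 2 is a summary in the rationale, so a lack of one-to-one correspondence is not itself an error; only the word *strictly* in the synopsis gives it weight. Nothing in the protocol shows that final pathology governs registration, or that known carriers are offered the technique. A remedy that could equally be met by tightening the criteria or by dropping one adverb does not alter the design or the analysis.

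**Conclusion.** No change to the plan follows. The textual observations are correct, but they amount to a clerical slip (the lost word in exclusion 2) and a gap in detail (already known BRCA1/2 status) that a single centre would fill sensibly from its own section 2.

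The effect is probably small and cannot be quantified, because the protocol gives neither the number of such patients nor their relapse risk. No direction of effect is claimed. The endpoint, the reference range, the planned number of about 150 patients and the 10-in-150 warning figure are untouched.

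The conclusion rests on three assumptions: that the recommended criteria in 6.4 are the ASTRO indication summarised in section 2; that the missing noun in exclusion 2 is emboli; and that exclusion 2 is judged on what is known at registration. Each is the most natural reading, and none is stated outright. If 6.4 in fact meant section 5, the wording would matter more, but the document still would not show how many patients it affected.
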